#### Center for International Blood and Marrow Transplant Research (CIBMTR) Data

**Reporting:** Centers participating in BMT CTN trials must register pre and post-transplant outcomes on all consecutive hematopoietic stem cell transplants done at their institution during their time of participation to the Center for International Blood and Marrow Transplant Research (CIBMTR). Registration is done using procedures and forms of the Stem Cell Transplant Outcomes Database (SCTOD). (Note: Federal legislation requires submission of these forms for all US allotransplant recipients.) Additionally, CIBMTR pre- and post- transplant Report Forms must also be submitted for all patients enrolled on this trial according to the randomization assigned to the patient at the time of initial registration with the CIBMTR. Long-term follow-up of patients on this study will continue through routine CIBMTR mechanisms.

#### 4.4. Assessments

All assessments are considered standard-of-care unless identified below by "\*."

#### Prior to Enrollment/Randomization

The following pre-enrollment/randomization assessments must be completed within the designated timeframe listed below.

- 1. Protocol-required 5 ml of blood (red top for serum) for the determination of biomarker risk status collected immediately prior to enrollment/randomization.
- 2. Complete acute GVHD staging and grading information including assessments of rash, diarrhea, nausea/vomiting, weight and liver function tests; Biopsy (if done) of involved tissue (standard of care, not research) within 24 hours prior to enrollment.
- 3. Recording of all systemic immune suppressive therapy (as appropriate: tacrolimus, cyclosporine, etc.), as well as topical agents within 24 hours prior to enrollment.
- 4. History and physical exam including height and weight, patient/disease/transplantation baseline variables within 7 days prior to enrollment.
- 5. CBC with differential, platelet count within 7 days prior to enrollment.
- 6. Liver function tests (bilirubin, alkaline phosphatase, AST, ALT) plus creatinine within 7 days prior to enrollment.
- 7. Pregnancy test per institutional practice (if applicable) within 30 days prior to enrollment.

The 5 ml blood sample for biomarker analysis must be shipped as soon as possible after randomization to the Biomarker Laboratory of the Icahn School of Medicine at Mount Sinai (see Appendix B).

Prior to Initiation of Study Therapy

Baseline assessments must be completed within 48 hours prior to initiation of study therapy unless otherwise indicated.

- 1. Karnofsky or Lansky Performance Status
- 2. Toxicity assessment
- 3. Baseline patient-reported outcome measures (M.D. Anderson Symptom Inventory, FACT-BMT, SF-36, or PedsQL (Pediatrics)\* Only English speaking adult and pediatric patients, and Spanish speaking adult patients are eligible to participate in the Health Quality of Life (HQL) component of this trial. Patients >18 years will complete the FACT-BMT, MOS SF-36 and MDASI instruments. Patients ≥ 8 years through 18 years will complete the PedsQLTM Stem Cell Transplant Module.
- 4. OPTIONAL 40 mL blood sample for research laboratory studies (see Appendix B) \* Patients with weight < 13 kg will have 3 mL/kg collected.

Baseline assessments required to be done as close to enrollment (day 0) as possible

- 1. Baseline myopathy assessments\* (may be done up to 96 hours after enrollment)
  - a. Hip Flexor and Quadriceps Strength via handheld dynamometer
  - b. Two Minute Walk Test
  - c. 5-time Sit-to-Stand
  - d. Adult Myopathy Assessment Tool (AMAT)
- 2. Fasting lipid profile (may be done up to 96 hours after enrollment)

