# 2.5. Treatment Plan

#### 2.5.1. Randomization

A 5 mL blood sample (red top tube) for Ann Arbor Scoring must be collected from the patient prior to enrollment/randomization in AdvantageEDC (see section 2.5.2). Upon confirmation of eligibility in AdvantageEDC, the study participant will be randomized in a 1:1 fashion to receive either sirolimus or prednisone. Study treatment (sirolimus/prednisone) should be initiated as soon as possible after randomization. A maximum of 24 hours from randomization to first dose of study medication is allowable.

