# **3.3.7.** Patient-reported Outcomes

These instruments will be completed by patients at enrollment, Day 56, 6 months, and 12 months. Only English speaking adult and pediatric patients, and Spanish speaking adult patients are eligible to participate in the Health Quality of Life (HQL) component of this trial. Patients >18 years will complete the FACT-BMT, MOS SF-36 and MDASI instruments. Patients ≥ 8 years through 18 years will complete the PedsQLTM Stem Cell Transplant Module. Surveys are completed by participants using self-completed instruments as a first choice. If this method of data collection is not possible, then surveys and response options may be read verbatim to participants, either in person or over the phone, to collect data. The method of survey completion, the date, and the language will be recorded in the database. Surveys may not be completed by surrogates.

Change in patient-reported outcomes from enrollment to Day 56 and 6 months will be calculated.

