#### 4.2. Enrollment/Randomization

Patients will be enrolled/randomized onto the study using the BMT CTN Advantage Electronic Data Capture (EDC). Patients will be randomized to Sirolimus versus Prednisone in a 1:1 ratio. The following procedures shall be followed:

- 1. An authorized user at the clinical center completes the initial screening by entering patient demographics and Segment A information (consent date, inclusion/exclusion criteria and confirmation that 5 mL of blood has been collected for Ann Arbor Scoring) on the Eligibility Form.
- 2. If the patient is eligible, a study number and random treatment assignment is generated.
- 3. A visit schedule based on enrollment date is displayed for printing.
- 4. Immediately after randomization, the 5 ml blood sample will be shipped priority overnight for early morning arrival at the Biomarker Laboratory of the Icahn School of Medicine at Mount Sinai for biomarker analysis.

If a connection is interrupted during a randomization session, the process is completely canceled and logged. A backup manual registration and randomization system will also be available to provide for short-term system failure or unavailability.

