### 5. STATISTICAL CORRELATIONS

#### 5.1. Study Design

The study is designed as a Phase II randomized, open label, multicenter trial to identify whether sirolimus is a potential alternative to prednisone as an up-front treatment for patients with standard risk acute GVHD (defined by both refined Minnesota standard clinical risk and AA1/2 biomarker risk group). The hypothesis is that sirolimus will produce comparable response rates while also reducing steroid burden in this population. As this is the first trial prospectively assessing sirolimus in a multicenter setting, the trial is not designed to formally declare non-inferiority but rather to estimate the difference in response rates between the sirolimus arm and the prednisone (or standard of care) arm. Estimation of this difference along with establishing more precise estimates for a key secondary endpoint with a response definition incorporating a measure of steroid burden (requirement a patient is on less than 0.25 mg/kg at Day 28) will allow assessment of sirolimus as a potential upfront treatment for GVHD response.

Patients will be randomized to either sirolimus or prednisone. The primary endpoint is complete or partial response (relative to their GVHD status on the day of randomization) on Day 28 post-randomization with secondary endpoints assessing alternate definitions of efficacy, safety, steroid burden and quality of life. The target enrollment is 120 eligible, randomized AA1/2 patients. One hundred and fifty patients are expected to be randomized as approximately 20% of randomized patients will have AA3 status results or missing biomarker results and be removed from the primary analysis (see the Primary Endpoint Section for details).

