### **1.5 Response Variables and Data Collection Time Points**

The response variables for this study include the primary, secondary, and safety endpoints. The primary endpoint is CR/PR at Day 28. Secondary endpoints include:

- CR/PR at Day 28 with steroid dose of 0.25mg/kg/day or less
- Disease response
- Treatment failure
- Chronic GVHD
- Systemic infection
- Event-free survival
- Overall survival
- Disease-free survival
- GVHD-free survival
- Non-relapse mortality
- Steroid dose
- Topical steroid therapy
- Discontinuation of immune suppression
- EBV-associated lymphoproliferative disorder
- Hyperglycemia
- Functional myopathy
- Hyperlipidemia
- Thrombotic microangiopathy
- CMV reactivation
- Patient-reported outcomes

Safety endpoints included mortality, toxicity, and adverse events. Safety monitoring will be conducted per protocol schedule as described in Section 2.4 of this SAP. Adverse events will be reported per the BMT CTN (Manual of Procedures) MOP.

Definitions for each endpoint are described in detail in the protocol and in section 4 of this SAP.

Participants are required to complete both pre-randomization and post-randomization assessments. Pre-randomization assessments must be performed prior to and as close as possible to the participant's enrollment / randomization on the trial. Post-randomization assessments occur weekly up to Day 56 and then occur at Day 90, 180,

and 365 post-randomization. Data from these evaluations are collected on calendar-driven clinical forms. Deaths, infections, hospitalizations, and adverse events are reported on event-driven clinical forms.

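### Baseline patient-reported outcomes may be completed up to 24 hours after the open-label arm is known, so the reported change from enrollment can carry a reaction to the assignment

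*Protocol*

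**What the plan says.** Protocol 4.4 has two baseline lists. The first, Prior to Enrollment/Randomization, includes the biomarker sample, prior immune suppression, laboratory tests and acute GVHD staging, the last of these "within 24 hours prior to enrollment". The second, Prior to Initiation of Study Therapy, holds performance status, toxicity, the PROs and an optional research sample. For this second list the rule is "Baseline assessments must be completed within 48 hours" before therapy starts. Table 4.4 keeps the split: GVHD evaluation is marked in the first baseline column, PROs and performance status in the second.

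Three other statements settle when the arm is known.
- Protocol 4.2: "If the patient is eligible, a study number and random treatment assignment is generated". Enrollment and randomization are one step.
- Protocol 5.1: "The study is designed as a Phase II randomized, open label, multicenter trial to identify whether" sirolimus is a potential alternative. There is no blinding.
- Protocol 2.5.1: "A maximum of 24 hours from randomization to first dose of study medication is allowable".

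On use, Protocol 3.3.7 states "These instruments will be completed by patients at enrollment, Day 56, 6 months, and 12 months" and then "Change in patient-reported outcomes from enrollment to Day 56 and 6 months will be calculated". Exploratory objective 7 (Protocol 2.3.3) extends the change to 12 months. Protocol 5.2.6 item 10 and SAP 4.3.10 compare scores between arms at each time point by two-sample t test. Exhibit 1501-22 shows a p-value on every row, baseline included.

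SAP 1.5 says "Pre-randomization assessments must be performed prior to and as close as possible to" enrollment/randomization, but does not list which assessments these are.

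**The concern.** A baseline is a sound reference for change only if the assignment cannot have influenced it. Here the patient may answer symptom and quality-of-life questions knowing whether the treatment is prednisone at 2 mg/kg/day or sirolimus. Protocol 3.3.7 also lets staff read the questions aloud, and they may know the arm too. Relief, disappointment or expectation at that moment would enter the reference value and pass, with the sign reversed, into the change from enrollment.

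At stake is how the PRO change can be read in a trial whose rationale includes sparing patients the burden of steroids. The baseline row of Exhibit 1501-22 also loses its usual meaning: if some forms follow allocation, a difference there can no longer be put down to chance imbalance alone. The problem might not be traceable afterwards, because Protocol 3.3.7 lists method, date and language as recorded items but not the time of completion.

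**Working it through.** **Timing.** Let the first dose fall T hours after randomization, with T from 0 to 24 (Protocol 2.5.1). The 48-hour window then runs from T − 48 to T relative to randomization, and the share of it after allocation is T/48.

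| First dose (T) | Permitted window | Share after allocation |
|---|---|---|
| 0 h | −48 to 0 h | 0/48 = 0% |
| 12 h | −36 to +12 h | 12/48 = 25% |
| 24 h | −24 to +24 h | 24/48 = 50% |

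A form can therefore be up to 24 hours late relative to allocation. These are shares of the permitted time. They are not forecasts of how many forms would be late.

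**Does other text close the gap?** The phrase at enrollment in Protocol 3.3.7 does not, because enrollment and assignment happen in the same step. SAP 1.5 does not, because it names no items, and Table 4.4 marks the PROs in the second baseline column.

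**Which outputs are reached?** Let s be the between-arm difference in mean baseline caused by the assignment, in SD units, and r the correlation of baseline with follow-up.
- Follow-up scores alone (the planned t tests): bias 0.
- Change from enrollment (to be calculated): bias −s.
- A baseline-adjusted comparison (not in the plan): bias −r·s.
- Baseline row of Exhibit 1501-22: shifted by s.

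**Illustration.** The plan gives no figure to reproduce. The inputs s = 0.1 to 0.3 and r = 0.3 to 0.7 are assumptions. The figure of 60 per arm is the protocol's primary-analysis number, and fewer will have PRO data. In SD units, SE(change) = √(2(1−r))·√(2/n) and SE(adjusted) = √(1−r²)·√(2/n). With no true effect, the two-sided 5% rejection probability is Φ(−1.96 + d) + Φ(−1.96 − d), where d = |bias|/SE.

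Example with n = 60, r = 0.5, s = 0.2:
- Change: SE = 1 × √(2/60) = 0.183, d = 0.2/0.183 = 1.095, rejection 19.5%.
- Adjusted: SE = 0.866 × 0.183 = 0.158, bias 0.5 × 0.2 = 0.1, d = 0.632, rejection 9.7%.

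| n = 60 per arm, r = 0.5 | s = 0.1 | s = 0.2 | s = 0.3 |
|---|---|---|---|
| Change-score test | 8.5% | 19.5% | 37.6% |
| Baseline-adjusted test | 6.2% | 9.7% | 15.8% |

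Over r = 0.3 to 0.7 the change-score range is 7.5% to 56.4% and the adjusted range 5.3% to 36.4%. With 40 per arm the ranges are 6.7% to 41.0% and 5.2% to 26.0%.

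**Dilution.** s is an arm-mean difference. If half the forms followed allocation, s = 0.3 would need 0.3/0.5 = 0.6 SD among those patients.

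**The case against.** The strongest reply is that the planned PRO tests do not use the baseline. Protocol 5.2.6 item 10, SAP 4.3.10 and Exhibit 1501-22 compare scores at each time point, and the weighted analysis estimates means at each time point. A reader might infer from the rejection rates above that the trial's follow-up PRO tests have inflated error. The documents do not support that: no change-score or baseline-adjusted test is specified, and a shifted baseline leaves a comparison of follow-up scores unbiased. This reply stands, and it confines the point to the change from enrollment and the baseline comparison.

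A reader might also extend the point to performance status, which has the same window. That does not hold as an analysis concern. Performance status has no change-from-enrollment endpoint, and SAP 3.1 takes the baseline value from the CIBMTR database.

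SAP 1.5 can be read as placing all baseline work before randomization, in which case the protocol and SAP merely differ in wording. This stands only in part: the SAP names no items, while the protocol's list and table explicitly place the PROs elsewhere.

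Finally, treatment is to start as soon as possible, which shortens the gap, and the window equally allows completion before randomization. Both are true. They limit how often the problem would arise, but no text prevents it.

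**Conclusion.** The point holds in a limited form. The protocol permits baseline PROs up to 24 hours after the arm is known, so the reported change from enrollment and the baseline between-arm comparison can reflect reaction to the assignment. The fault is a missing requirement. The documents do not show that late completion would be common, how large a shift would be, or in which direction. The rejection rates depend on assumed values of s, r and n, and would apply to a treatment comparison only if a change-score or baseline-adjusted test were used.

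It would be wrong to read this as a threat to the main result. The GVHD staging that serves as reference for the Day 28 response is taken before enrollment, and the PROs are exploratory. This is a cheap improvement.

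**What to change.** In Protocol 4.4, move the PROs from the list tied to the start of therapy to the pre-randomization list, and shift their X in Table 4.4 to the first baseline column, so that they are completed after consent and before the assignment is displayed. Performance status need not move. Record the completion time relative to randomization as well as the date. In SAP 4.3.10, add a sensitivity analysis that leaves forms completed after allocation out of the change-from-enrollment summary.

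With every form completed before allocation, the post-allocation part of the window is 0 hours and bias from this source is zero. The cost is protocol wording, one extra data field and some burden before randomization: for adults 19 + 27 + 23 + 36 = 105 items across MDASI, FACT-BMT and SF-36. A contact already exists at that stage for consent, staging and the blood sample. The downside is that a few baseline forms may be missed when treatment is urgent.

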#### Post-Randomization

The following post-randomization assessments are required of all patients, regardless of therapy received.

- 1. Karnofsky or Lansky performance status at Days 56, 90, 180 and 365
- 2. Complete acute GVHD staging and grading information including assessments of rash, diarrhea, nausea/vomiting, weight and liver function tests weekly through Day 56; Day 90, 6 and 12 months
- 3. Chronic GVHD evaluation (if present) Day 28, 56, 90, and 6 and 12 months
- 4. CBC with differential, chemistry (including liver function tests) weekly through Day 56; Day 90, 6, and 12 months
- 5. Fasting lipid profile at Day 28, 56, and 6 months
- 6. Toxicity evaluation weekly through Day 56; Day 90, 6 months and 12 months
- 7. Recording of all systemic immune suppression, including steroid dose and drug levels (as appropriate for sirolimus, cyclosporine, tacrolimus) weekly through Day 56, Day 90, 6, and 12 months. Second-line immune suppressive therapy (therapy beyond initial

randomized therapy of either sirolimus or prednisone) should be recorded at each of these time points.

- 8. Use of topical (skin, GI) steroid agents weekly through Day 56; Day 90, 6 and 12 months.
- 9. Data on systemic infections, and EBV PTLD (or EBV requiring therapy), recorded as per the BMT CTN (Technical) MOP through 12 months.
- 10. EBV & CMV monitoring as per institutional practice.
- 11. Myopathy assessments at Day 56 and 6 months.\*
  - a. Hip Flexor and Quadriceps Strength via handheld dynamometer
  - b. Two Minute Walk Test
  - c. 5-time Sit-to-Stand
  - d. Adult Myopathy Assessment Tool (AMAT)
- 12. Patient reported outcomes (M.D. Anderson Symptom Inventory, FACT-BMT, SF-36, or PedsQL (Pediatrics)) at Day 56, 6 months and 1 year.\* Only English speaking adult and pediatric patients, and Spanish speaking adult patients are eligible to participate in the Health Quality of Life (HQL) component of this trial. Patients >18 years will complete the FACT-BMT, MOS SF-36 and MDASI instruments. Patients ≥ 8 years through 18 years will complete the PedsQLTM Stem Cell Transplant Module.
- 13. OPTIONAL 30-40 mL blood samples for research laboratory studies at Day 7, 28, and 56 (see Appendix B).\* Patients with weight <13 kg will have ≤3 mL/kg collected at each individual time point.

#### Table 4.4 – REQUIRED ASSESSMENTS

	Pre- Randomize	Pre- Pre- Days Post Randomization											
	Base	line	7*	14*	21*	28*	35*	42*	49*	56 *	90**	180***	365***
History and physical exam	Х												
Pregnancy test (if applicable)	Х												
Karnofsky/Lansky performance status		Х								Х	Х	Х	Х
Acute GVHD evaluation	Х		Х	Х	Х	Х	Х	Х	Х	Х	Х	Х	Х
Chronic GVHD evaluation						Х				Х	Х	Х	Х
CBC with differential, platelet count	Х		Х	Х	Х	Х	Х	Х	Х	Х	Х	Х	Х
Basic chemistry (creatinine)	Х		Х	Х	Х	Х	Х	Х	X-	Х	Х	Х	Х
Liver function tests (alkaline phosphatase, bilirubin, AST, ALT)	Х		Х	Х	Х	Х	Х	Х	Х	Х	Х	Х	Х
Fasting lipid profile		X 				Х				Х		Х	
Toxicity and AE evaluation		Х	Х	Х	Х	Х	Х	Х	Х	Х	Х	Х	Х
Recording of all systemic immune suppression, including steroid dose	Х		Х	Х	Х	Х	Х	Х	Х	Х	Х	Х	Х
Drug level monitoring (e.g. tacrolimus, cyclosporine)	Х	Х	Х	Х	Х	Х	Х	Х	Х	Х	Х	Х	Х
Use of second-line immune suppressive therapy			Х	Х	Х	Х	Х	Х	Х	Х	Х	Х	Х
Use of topical agents	Х		Х	Х	Х	Х	Х	Х	Х	Х	Х	Х	Х
Malignancy relapse, death			Х	Х	Х	Х	Х	Х	Х	Х	Х	Х	Х
Systemic infections	Х		Х	Х	Х	Х	Х	Х	Х	Х	Х	Х	Х
EBV PTLD, or EBV requiring therapy			Х	Х	Х	Х	Х	Х	Х	Х	Х	Х	Х
CMV reactivation requiring therapy			Х	Х	Х	Х	Х	Х	Х	Х			
Myopathy assessments		X 								Х		Х	
Patient-reported outcomes: MDASI, FACT-BMT, MOS SF-36, PedsQL 		Х								Х		Х	Х
REQUIRED 5 mL blood sample for Ann Arbor Panel Scoring collection	X 												
OPTIONAL Research blood samples for ancillary studies (see Appendix B) 		Х	Х			Х				Х			

\* +/- 3 days to allow for scheduling flexibility, holidays, etc. Subsequent visits through Day 56 must be scheduled weekly.

\*\* +/- 14 days to allow for scheduling flexibility

\*\*\* +/- 28 days to allow for scheduling flexibility

 The fasting lipid panel may be done up to 96 hours after enrollment.

 Myopathy assessments may be done up to 96 hours after enrollment.

 Only English speaking adult and pediatric patients, and Spanish speaking adult patients are eligible to participate in the Health Quality of Life (HQL) component of this trial. Patients >18 years will complete the FACT-BMT, MOS SF-36 and MDASI instruments. Patients > 8 years through 18 years will complete the PedsQLTM Stem Cell Transplant Module.

 Required blood sample for Ann Arbor Scoring must be collected prior to enrollment/randomization and shipped overnight immediately afterwards.

 Patients with weight < 13 kg will have  $\leq$ 3 mL/kg collected

#### 4.5. Weekly GVHD Monitoring

GVHD scoring will be performed weekly for 8 weeks from study entry. Days 0, 28 and 56 ( $\pm$ 3 days) scoring must be performed by direct observation at the Transplant Center. Evaluations at other time points may be performed by competent clinicians other than at the Transplant Center but Transplant Center is responsible for collecting all required data.

#### 4.6. Adverse Event Reporting

Adverse Event: An adverse event (AE) is any undesirable sign, symptom or medical condition or experience that develops or worsens in severity after starting the first dose of study treatment or any procedure specified in the protocol, even if the event is not considered to be related to the study.

Expectedness: An adverse event can be Expected or Unexpected

- **Expected adverse events** are those that have been previously identified as resulting from administration of the agent. For the purposes of this study, an adverse event is considered expected when it appears in the current adverse event list, the Investigator's Brochure, the package insert or is included in the informed consent document as a potential risk.
- Unexpected adverse events are those that vary in nature, intensity or frequency from information in the current adverse event list, the Investigator's Brochure, the package insert, or when it is not included in the informed consent document as a potential risk.

**Serious Adverse Event:** A serious adverse event (SAE), as defined by 21 CFR 312.32, is any adverse event that results in one of the following outcomes, regardless of causality and expectedness:

- Results in death
- Is life-threatening. Life-threatening means that the person was at immediate risk of death from the reaction as it occurred, i.e., it does not include a reaction which hypothetically might have caused death had it occurred in a more severe form.
- **Requires or prolongs inpatient hospitalization** (i.e., the event required at least a 24hour hospitalization or prolonged a hospitalization beyond the expected length of stay). Hospitalization admissions and/or surgical operations scheduled to occur during the study period, but planned prior to study entry are not considered SAEs if the illness or disease existed before the person was enrolled in the trial, provided that it did not deteriorate in an unexpected manner during the trial (e.g., surgery performed earlier than planned).
- **Results in persistent or significant disability/incapacity.** Disability is defined as a substantial disruption of a person's ability to conduct normal life functions.
- Is a congenital anomaly or birth defect; or
- Is an important medical event when, based upon appropriate medical judgment, it may jeopardize the participant and require medical or surgical intervention to prevent one of

the outcomes listed above. Examples of such medical events include allergic bronchospasm requiring intensive treatment in an emergency room or at home; blood dyscrasias or convulsions that do not result in inpatient hospitalization, or the development of drug dependency or drug abuse.

Medical and scientific judgment should be exercised in deciding whether expected reporting is also appropriate in situations other than those listed above. For example, important medical events may not be immediately life threatening or result in death or hospitalization but may jeopardize the subject or may require intervention to prevent one of the outcomes listed in the definition above (e.g., suspected transmission of an infectious agent by a medicinal product is considered a Serious Adverse Event). Any event is considered a Serious Adverse Event if it is associated with clinical signs or symptoms judged by the investigator to have a significant clinical impact.

